9.2.3.2 Patient reported outcome scoring

Section modified by Amendment 2 (Modification 3)

The PRO instruments used to measure key outcomes in this study are scored in the following ways:

PROMIS Scale v1.0—Pain Intensity 3a: For measurements of pain intensity informing the pain event outcome in this study, Bayer will employ individual T-Scores. The T-scores are referenced to the US population and easily derived from totaled raw scores in line with published, publically available PROMIS scoring criteria (4).

The pain intensity score, like other PROMIS instrumentation, was designed using Item Response Theory techniques and can be more precisely scored on the basis of item-level calibrations and response pattern scoring. For analysis other than screening alerts and identification of unreported events, the item-level or “theta” scores may be used as an alternative in exploratory analyses.

PROMIS Scale v1.0—Pain Interference 8a: Scoring for the Pain Interference measure is designed in line with the same criteria as those for Pain Intensity (5). A T-score threshold will be one basis for triggering clinical alerts (see below). Additional exploratory analyses may alternatively use response pattern scoring and using the θ parameter estimate as the individual score.

AMSS: The scoring for the AMSS is outlined in an article reporting the initial validation of the instrument (6). The AMSS was designed using standard Classical Test Theory techniques and all scores are based on raw score totals. Per the initial validation, 13 items are included with a possible raw score total ranging from 0 to 42 points. Individual scores are calculated as the percentage of the maximum possible attained. Clinically meaningful thresholds are discussed below.

MOS SF-36 v2: The SF-36 is a generic health-related quality of life measure that is not focused on a particular disease or condition. This assessment scores eight distinct health domains and provides psychometrically-based physical component summary and mental

component summary scores. Domains include physical function, role-physical, bodily pain, mental health, role-emotional, social functioning, vitality, and general health perceptions.

FSQ: This is a validated questionnaire based on the premise of the importance of an altered central nervous system in processing of pain and other somatic symptoms, or a “centralized pain state” (7). While initially studied in fibromyalgia, research has found that the centralized pain state plays an important role in many chronic pain cohorts, including chronic pelvic pain.

Supplemental PRO Questionnaires: The Supplemental PRO Questionnaires consist of a series of questions covering several different symptoms (depression, anxiety, nausea/vomiting, pruritus, rash, pain in extremities, fatigue, hair loss, dysgeusia, dental problems, weight change). Details about the creation of these questionnaires and information about validation, if applicable, as well as the questionnaires for these events are provided in Appendix 17.8.

9.2.3.3 Patient reported outcome measurement thresholds

Section modified by Amendment 2 (Modification 3).

This study will first employ a medically conservative and sensitive screening threshold to ensure capture of events in subjects that may not report concerns about their pain or bleeding to site investigators. The screening thresholds reflect the clinical judgment of Bayer investigators. Secondly, a more specific preliminary threshold for reporting AEs on the basis of PRO scores alone will be employed. These thresholds reflect scoring derived in instrument development and research experience with the scales.

For the Supplemental PRO Questionnaires related to mental health, a total response greater than or equal to 3 for either set of questions will prompt notification of the investigator; for the Supplemental PRO Questionnaires related to nausea/vomiting, any single response greater than or equal to 3 will prompt notification of the investigator. For the pruritus 5D itch scale, rash, pain in extremities, and fatigue scales, any response greater than or equal to 4 will prompt notification of the investigator. These thresholds were selected to ensure that subjects receive appropriate follow-up if they report medically important symptoms. There are no threshold triggers for hair loss, dysgeusia, dental care, or weight change. Upon notification about a threshold trigger on a Supplemental PRO Questionnaire, an investigator will assess the subject as he/she deems medically appropriate. If after assessment it is concluded that an AE has occurred, it must be captured on the appropriate AE eCRF. Additional information about these questionnaires is provided in Appendix 17.8.

9.2.3.4 Screening thresholds

Section modified by Amendment 1 (Section 16.1).

PROMIS Scale v1.0—Pain Intensity 3a: Any subject response of 3 or higher on Item PAINQU6, “Worst Pain,” or a total T-Score above 50 (i.e., above the US population mean) of PRO response will trigger an electronic communication (via email) to the site. If the subject has not previously received medical attention and evaluation for her pain by the site investigator or staff, the investigator will arrange for a timely (as assessed by the investigator

and site expertise) investigation of the subject's pain to determine if the subject is experiencing a pain AE as defined in this protocol.

PROMIS Scale v1.0—Pain Interference 8a: Subjects reporting a rating of 4 (“Quite a bit”) or higher on any item or having a T-Score above 50 on the Pain Interference short form will trigger communication about the result to site investigators. A T-score greater than 60 at any cross-section will also trigger a preprogrammed communication to the site investigator. If the subject has not previously had her pain assessed by the site investigator, these scores will signal the need to do so in a timely manner.

AMSS: The following item thresholds reported by a subject at a cross-sectional administration will serve to trigger communication to the site: Question 1 (≥ 2 —“Between 8 and 10 days”), Questions 2 to 3 (*no trigger associated*), Question 4 (≥ 2 —“Heavy”), Question 5 (≥ 3 —“Between 7 and 10 days”), Question 7 (≥ 1 —“Soiling / staining of your outer clothes / over garments”), Question 8 (≥ 1 —“I could continue to work, but my work suffered”), Question 9 (≥ 1 —“Yes, usually or part of one day”), Questions 10 to 11 (≥ 2 —“Moderately affected by heavy periods”), Questions 12 to 13 (*no trigger associated*). Additionally, an AMSS total score greater than 40 will serve to trigger communication to the site and the site will determine if the subject requires an unscheduled visit for her complaint.

[figure not shown]
9.2.3.4.1 Self-report event thresholds

PROMIS Scale v1.0—Pain Intensity 3a: A subject T-Score greater than or 60 will be flagged, identified, and reported as a “PRO-identified pain intensity event.” This threshold value reflects a score one SD above the US population mean derived in developing the instrument.

PROMIS Scale v1.0—Pain Interference 8a: A subject T-Score greater than or equal to 60 will be flagged, identified, and reported as a “PRO-identified pain interference event.” This threshold value reflects a score one SD above the US population mean derived in developing the instrument. Authors showed the distribution of T-Scores in a population of subjects with chronic pain due to various conditions, providing a useful demonstration for the applicability of this cut-point ([Figure 9–1](#)).

AMSS: A subject score greater than or equal to 40 points will be flagged, identified, and reported as a “PRO-identified AUB event.” The threshold is approximated from 3 “known groups” reported in the research literature, using an estimate below the lower bound of the SD of the largest trial sample where we are most confident about scoring ([Table 9–3](#)) (6).

Figure 9–1 Distribution of PROMIS Pain Interference T-Scores in a Population with Chronic Pain

PROMIS=patient reported outcome measurement information system.

Note: Adult respondents having at least one chronic pain condition for the past 3 months, taking the PROMIS web survey posted online. Participants answered the entire candidate 47-item candidate bank from which the short form proposed for use is derived, validated, and normed.

Table 9–3 “Known Group” Means and Supporting Statistics for Estimating Preliminary AMSS Self-Report Event Threshold

Sample	N	Mean	SD [Range]	Possible AUB Threshold
Baseline AMSS, premenopausal women with AUB later treated with hydrothermablation (9)	47	47.8	17.4	30.4
Baseline AMSS, premenopausal women with “dysfunctional uterine bleeding” assigned for hysterectomy (10)	114	57.3	15.5	41.8
Baseline AMSS, premenopausal women with “dysfunctional uterine bleeding” assigned for endometrial ablation (10)	123	59.1	15.5	43.6
Baseline AMSS, premenopausal women with “heavy uterine bleeding” related to leiomyomas, later treated with uterine artery embolization (11)	6	53	[51.1-76.7]	51.1
Baseline AMSS, premenopausal women with “heavy uterine bleeding” related to leiomyomas later treated with uterine artery occlusion (11)	8	54	[51.1-69.8]	51.1

AMSS=Aberdeen Menorrhagia Severity Scale, AUB=abnormal uterine bleeding, SD=standard deviation.

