5.2 Endpoints and variables

5.2.1 Main endpoints

Section modified by Amendment 1 (Section [16.1](#)) and Amendment 2 ([Modification 3](#), [Modification 4](#), [Modification 5](#), [Modification 7](#)).

- **Pain:** The proportion of subjects reporting AEs of chronic lower abdominal and / or pelvic pain after insertion of Essure System compared to the proportion of subjects reporting AEs of chronic lower abdominal and / or pelvic pain after laparoscopic tubal sterilization. Total incidence of pain events will be based on AE reporting. If a potential pain event is spontaneously reported outside of a scheduled visit or scheduled patient-reported outcome (PRO) tool administration, the pain PRO tools (Patient-Reported Outcomes Measurement Information System [PROMIS] Scale V1.0 – Pain Intensity 3a and PROMIS Scale V1.0 – Pain Interference 8a Participant Format; see Section [9.2.3](#)) will be administered off-schedule in order to characterize pain intensity and interference. If during the course of a scheduled PRO administration (see [Table 9–2](#) and Section [9.2.3](#)) the subject reaches a preset threshold for pain on a PRO tool, even if she has not spontaneously reported a pain event to the investigator, the investigator will be alerted and instructed to investigate this finding in order to determine whether or not an AE has occurred. Standard criteria for AE assessment (e.g., new or worsening symptom) will be used and all investigators will be trained on standard AE assessment.

The preset thresholds that will trigger investigation of pain as an AE are as follows: on the PROMIS Pain Intensity Scale, a score of 3 (moderate intensity) for the ‘pain at its worst’ question will trigger investigation regardless of the other scores or results of the PROMIS Pain Interference Scale. For PROMIS Pain Interference Scale, a t-score of ≥ 60 (which corresponds to a raw score of ≥ 22) or any single item raw score of ≥ 4 will trigger investigation regardless of the results of the PROMIS Pain Intensity Scale. Section [9.2.3](#) includes justification for these thresholds. Not all reports of pain that are reported on the PRO tool will be considered AEs. This is particularly notable in the case of a subject who has pre-existing pain that continues to be unchanged post-sterilization procedure.

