6.2 Exclusion criteria

Section modified by Amendment 1 (Section 16.1) and Amendment 2 (Modification 10, Modification 11).

1. Subjects who are post-menopausal;
2. Subjects suspected of being or who are confirmed to be pregnant;
3. Subjects post-partum or having undergone pregnancy termination ≤ 6 weeks prior to scheduled procedure (Note: subjects may be screened and consented for the study prior to 6 weeks post-partum / post pregnancy termination; however, PRO tools must be administered > 6 weeks post-partum / pregnancy termination and the sterilization procedure must occur > 6 weeks post-partum / pregnancy termination);
4. Subjects uncertain about ending fertility;
5. Subjects with an active upper or lower genital tract infection;
6. Subjects with gynecologic malignancy (suspected or known);

7. Subjects who have had an attempted prior sterilization procedure (either laparoscopic or hysteroscopic);
8. Subjects scheduled to undergo concomitant intrauterine or laparoscopic procedures at the time of insert placement (intrauterine device removal/insertion is not considered a concomitant procedure) or laparoscopic sterilization;
9. Subjects with unexplained vaginal bleeding;
10. Any diseases or conditions that might interfere with the conduct of the study or the interpretation of the results (subjects with pre-existing conditions such as pelvic pain, autoimmune disease, or menorrhagia may be included at the discretion of the principal investigator);
11. Subjects who are direct employees or immediate family members of the Sponsor company or site investigators.

For the Essure group only:

12. Subjects who can have only one insert placed (including contralateral proximal tubal occlusion or suspected unicornuate uterus);
13. Subjects who have a known abnormal uterine cavity that makes visualization of the tubal ostia impossible and / or abnormal tubal anatomy or previous tubal ligation (including failed ligation);
14. Subjects who have had total or partial salpingectomies;
15. Subjects who are currently taking corticosteroids or immunosuppressive therapy;
16. Subjects with a known allergy to all contrast media available for use in HSG.

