**Table 2 - Outcome endpoints and variables collected during treatment**

	Endpoint/Variable
Main Endpoints	
 
Subjects reporting AEs of chronic lower abdominal and/or pelvic pain after sterilization procedure
 
Subjects reporting AEs of abnormal uterine bleeding after sterilization procedure
 
Subjects with reported allergic/hypersensitive reactions
 
Subjects with newly diagnosed autoimmune disorders
 

	Endpoint/Variable
	
 
Subjects undergoing invasive gynecologic surgery (e.g., device removal or hysterectomy) after sterilization procedure (excluding second Essure placement attempts)
 

Patient Reported Outcomes	
 
MOS SF-36 (Version 2) which includes eight distinct health domains (physical function, role-physical, bodily pain, mental health, role-emotional, social functioning, vitality, and general health perceptions) and physical component summary and mental component summary scores
 
PROMIS Scale V1.0—Pain Intensity 3a, raw score, T-Scores, percentages of subjects who had T-Scores more than 50 and 60
 
PROMIS Scale V1.0—Pain Interference 8a, raw score, T-Scores, percentages of subjects who had T-Scores more than 50 and 60
 
AMSS and two intermenstrual bleeding questions used to characterize bleeding in subjects undergoing Essure placement and laparoscopic tubal sterilization, total raw scores and individual score for each question, percentage of subject having total scores greater than 40
 
FSQ: to investigate if scores on this instrument (continuous and categorical) correlate with chronic pelvic pain over the course of the study
 
Supplemental PRO Questionnaires
 
Social Media Questionnaire
 

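### PRO-identified pain and bleeding events are defined by an absolute score with no baseline condition, so unchanged pre-existing symptoms are counted together with new ones

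*Protocol*

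**What the plan says.** Protocol 9.2.3.3 sets up two tiers of PRO threshold. The first is a sensitive screen that alerts the site. For the second, "a more specific preliminary threshold for reporting AEs on the basis of PRO scores alone will be employed". Protocol 9.2.3.4.1 then defines that second tier:

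- AMSS: "A subject score greater than or equal to 40 points will be flagged, identified, and reported as a" PRO-identified bleeding event.
- PROMIS Pain Interference: "A subject T-Score greater than or equal to 60 will be flagged, identified, and reported as a" PRO-identified event.
- PROMIS Pain Intensity: worded in parallel at a T-score of 60, although the comparison itself is incomplete ("A subject T-Score greater than or 60 will be flagged, identified, and reported as a").

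The AMSS value was chosen from women who already had abnormal bleeding, "using an estimate below the lower bound of the SD of the largest trial sample where we are most confident about scoring".

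SAP Table 2 lists, for the AMSS, the "percentage of subject having total scores greater than 40", and for each PROMIS scale the shares above 50 and above 60. It attaches no baseline condition. The SAP never uses the term PRO-identified event. SAP 6.4 restricts comparative analysis to the main endpoints, and SAP 6.4.6 makes longitudinal PRO analysis descriptive.

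Elsewhere the plan does take account of baseline. Protocol 5.2.1 says that not every pain report on the PRO tool will be an AE: "This is particularly notable in the case of a subject who has pre-existing pain that continues to be unchanged post-sterilization procedure". It says the same for pre-existing abnormal bleeding. Such women can be in the study, because under exclusion criterion 10 in protocol 6.2 "subjects with pre-existing conditions such as pelvic pain, autoimmune disease, or menorrhagia may be included at the discretion of the principal investigator". Baseline PRO scores are taken at the procedure visit (protocol 9.2.2, Table 9-2), and SAP 4.6.1 defines baseline as the last value at or before the index event.

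**The concern.** The pain and bleeding objectives are about symptoms that are new or have got worse. A score-only event is about symptoms that are present. A woman who enters with heavy periods and an AMSS of 50, and still scores 50 at Month 12, becomes a PRO-identified bleeding event although nothing has happened to her. If 9.2.3.3 is followed as worded, her score alone is also grounds for reporting an AE, whereas 5.2.1 leaves that decision to the investigator and singles out unchanged pre-existing symptoms as a case that may not qualify.

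What is at stake is the usefulness of a supportive summary. The study is open-label, and protocol 5.2.1 expects AE reporting to be open to outside influence. An event that does not pass through the investigator is therefore worth having beside the AE endpoints. It can play that part only if new crossings are separated from symptoms that were there before the procedure.

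**Working it through.** **1. The plan's own figures.** Table 9-3 takes the sample mean minus one SD as a possible bleeding threshold:

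- hydrothermablation sample (n = 47): 47.8 − 17.4 = 30.4
- hysterectomy sample (n = 114): 57.3 − 15.5 = 41.8
- endometrial ablation sample (n = 123): 59.1 − 15.5 = 43.6

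All three reproduce. The chosen value of 40 lies below the last two. For PROMIS, the population mean of 50 plus one SD of 10 gives 60, also as stated.

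**2. What a cut-off of 40 detects.** Assume normal scores, with P(score ≥ 40) = 1 − Φ((40 − mean)/SD):

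| Table 9-3 sample | z | P(score ≥ 40) |
|---|---|---|
| Hydrothermablation | (40 − 47.8)/17.4 = −0.45 | 67% |
| Hysterectomy | (40 − 57.3)/15.5 = −1.12 | 87% |
| Endometrial ablation | (40 − 59.1)/15.5 = −1.23 | 89% |

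These are baseline scores, so most women in those samples would count as events at any single administration with no change. For PROMIS the corresponding tail is 1 − Φ(1) = 16% of the reference population. That is an upper illustration, since the scales are given only after a positive pain screener.

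**3. Effect on a group comparison.** Let p be the share of each group entering with such bleeding and q the probability that such a woman exceeds the cut-off. Suppose nobody changes and other women do not cross. The apparent difference is then (p for Essure − p for laparoscopy) × q. With q from 0.67 to 0.89, each percentage point of baseline imbalance produces 0.67 to 0.89 points of apparent difference. With perfect balance it produces none, but the same pre-existing cases are then counted in both groups.

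**4. What a baseline condition achieves.** Unchanged women were simulated from the Table 9-3 means and SDs with an assumed within-woman correlation. The share who are below 40 at baseline and at or above 40 at one later visit is:

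- correlation 0.5: 15%, 8% and 7% (samples in the order above)
- correlation 0.9: 7%, 4% and 3%

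This compares with 67%, 87% and 89% when no baseline condition applies. Some false crossings remain. Among unchanged women who start below 40, the chance of a crossing at one later visit runs from 0.065/(1 − 0.674) = 20% (hydrothermablation, correlation 0.9) to 0.073/(1 − 0.890) = 66% (ablation, correlation 0.5).

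**The case against.** The strongest reply is that no planned inference uses these events. The main pain and bleeding endpoints rest on AE reporting under new-or-worsening criteria (protocol 5.2.1). The PRO objective is only to collect data, and the SAP keeps PRO analysis descriptive. That stands, and it limits the point to a supportive output.

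Three stronger readings are tempting, and the documents do not support them.

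- A reader might infer that the main endpoints are contaminated by prevalent symptoms. They are not, because they do not use the score cut-offs as events.
- A reader might infer that these are the only pain and bleeding outcomes free of investigator judgement, or that they merely measure who chose which procedure. SAP Table 2 also lists PROMIS and AMSS scores, the intermenstrual bleeding questions and SF-36 bodily pain, all self-reported. SAP 6.6.2 makes the matched set primary for PRO summaries. Pre-existing abnormal bleeding is a candidate matching variable in SAP Table 5, and pelvic pain is one in protocol 10.3.
- A reader might put a figure on the group difference. For example, 15% and 10% of women entering with heavy bleeding, 80% of whom exceed 40, would give 12% versus 8%. All three inputs are assumed, the example ignores matching, and the Table 9-3 women were selected for bleeding treatment, whereas this study excludes unexplained vaginal bleeding.

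It can also be said that a by-visit table could show the baseline share beside later shares. It could, but marginal shares do not show which women crossed.

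Finally, an event restricted to women below the cut-off at baseline would discard worsening among the rest, break matched pairs, and still pick up score fluctuation. Baseline AMSS is an imperfect anchor too: it has a three-month recall and may be completed just over six weeks after a birth. These objections are fair, and they are why the fix keeps the women above the cut-off and asks for no new event endpoint.

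**Conclusion.** The point holds for the PRO-identified events and for the SAP Table 2 threshold shares. Neither document gives them a baseline, change or new-onset condition, and the AE wording in 9.2.3.3 conflicts with 5.2.1. Unchanged pre-existing pain or bleeding is therefore labelled a post-procedure event.

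The size within this study cannot be stated from the documents. The 67% to 89% rests on normality and on samples of women treated for, or assigned to treatment for, bleeding. It describes the cut-off, not this population. Any between-group gap depends on the imbalance remaining after matching and could be zero. The main AE-based pain and bleeding endpoints are untouched. This is a repair to a supportive summary, worth making because the baseline scores are already in hand.

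**What to change.** 1. **Reconcile the protocol text.** Bring 9.2.3.3 into line with 5.2.1, so that a PRO score alone is not reported as an AE.
2. **Report crossings by baseline status in SAP Table 2.** For each scale and visit, give new crossings among women below the cut-off at the last pre-procedure assessment, counting a baseline pain-screener answer of *No* as below. For women already at or above it, give a baseline-by-visit shift table and the change from baseline score, so that worsening is kept.
3. **Keep it descriptive.** Present these tables beside the AE endpoints in the Full and Adjusted Full Analysis Sets. No new Kaplan-Meier or Cox analyses are needed.

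The classification also needs one cut-off on one scale. Protocol 5.2.1 and 9.2.3.4.1 use at least 40 for the AMSS, while 9.2.3.4 and SAP Table 2 use above 40; pain interference has the same split at 60. Protocol 9.2.3.2 scores the AMSS as a percentage of a 42-point maximum, while SAP Table 2 refers to raw totals: 40% is 0.40 × 42 = 16.8 raw points, whereas 40 raw points is 40/42 = 95% of the maximum. The Table 9-3 means exceed 42, so they must be percentages.

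The cost is a few extra tables and one derived variable per scale, with no new data collection. Denominators for new crossings will be smaller, and subsets by baseline status no longer preserve the 1:1 matched pairs. Some new crossings will be ordinary score fluctuation. The table notes should say so.
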